#### **Intervention Groups and Duration:**

All participants will receive either 120 mg of elinzanetant or matching placebo orally once daily, while staying on their current treatment, including their adjuvant endocrine therapy. There will be 2 arms in the study

- Elinzanetant for 52 weeks and optionally additional 2 years
- Placebo for 12 weeks, followed by elinzanetant for 40 weeks and optionally additional 2 years

**Data Monitoring/Other Committee:** Yes

10 MAY 2023 Page: 12 of 97

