4.1.2. Data Rules

Definition of baseline: The latest available valid measurement excluding unscheduled measurements at or before the start of treatment (for treated subjects) / randomization date (for randomized but not treated subjects). If the last observation available prior to randomization is the measurement from the Screening Visit, this would be used as the baseline value. In case a wash-out period was necessary, measurements taken during the prescreening visit will not be used as a baseline value unless specified otherwise.

Change from baseline: To calculate the absolute change from baseline the baseline value will be subtracted from the value under treatment/follow-up, i.e.,

Absolute change = post baseline value – baseline value.

Some parameters will be additionally analyzed as relative change defined as

Relative change = 100 * [(post baseline value – baseline value) / baseline value].

Derivation of intercurrent event (ICE): Intercurrent events that occurred from randomization date (for randomized but not treated subjects) / start of treatment (for treated subjects) to day 84 inclusive will be flagged.

version 3.0 Page: 24 of 87

For the "permanent discontinuation of randomized drug", "intake of prohibited medication having impact on efficacy" and "interruption/ discontinuation in intake of adjuvant endocrine therapy", if the ICE occurs on or before the 5th day of the week, it will be flagged for the respective week. If the ICE occurs on the 6th or 7th day of the week, it will be flagged from the following week. For example, if the participant permanently discontinues from the randomized drug on the 2nd day of week 4, the ICE will be flagged from week 4 onwards. If the discontinuation from the randomized drug occurs on the 6th day of week 4, then the ICE will be flagged from week 5 onwards. For the ICEs "intake of prohibited medication having impact on efficacy" and "interruption/ discontinuation in intake of adjuvant endocrine therapy", if the end date for the impact on efficacy occurs on the 1st or 2nd day of the week, the respective week should not be flagged. If the end date of impact on efficacy occurs on or after the 3rd day of the week, the week should be flagged.

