- From Week 4 onwards: a 2-week window will be used to map the available assessments to Week 4 (Days 15-28), Week 8 (Days 43-54*), or Week 12 (71-82*). A similar 2-week window will be used from Week 16 to Week 52. Within each 2-week-window, the last available assessment (i.e., the one closest to the scheduled assessment) will be used for mapping.
 - *Week 1 = Days 2-8; Day 8 (week 1), Days 55/56 (week 8) and Days 83/84 (week 12) are scheduled assessments, and no mapping would be required, therefore, these days are not considered in the window for mapping.
- In case an assessment is assigned to Week 2 or 3 and to Week 4, based on the above rules, it will be shown for Week 2 or 3 in the descriptive tables. The Week 4 assessment will only be used in the model-based analyses.
- Assessments from follow-up visits will be shown as follow-up in the descriptive tables, and the value mapped to a specific treatment week will only be used in the model-based analyses.
- In the descriptive tables, data collected after premature discontinuation of treatment will not be shown for the respective treatment week. Assessments occurring up to 2 days after discontinuation (inclusive) will still be considered under treatment and shown for the respective week. Out of the assessment collected post treatment discontinuation (+ 2 days), the one closest to the planned time point of follow-up (i.e. discontinuation date + 28 days) will be shown as follow-up assessment. In case two assessments are equally close to that date, the first one will be selected.

Laboratory values <X or >X: For laboratory values lower than a limit of detection X which are given as **<**X , half the value of X will be used for analysis (i.e., values reported as "**<**X", "**<**X.X", "**<**X.XX" or etc. the value for analysis used will be derived by "X/2", "X.X/2", "X.XX/2" etc). Differences between 2 values **<**X will be assigned values of 0. Ratios between 2 values **<**X will be assigned a value of 1. For values which are higher than a limit of detection Y, given as Y, the value of Y will be used for analysis.

Repeated measurements at the same visit after start of treatment: If more than one post-randomization measurement is available for a given visit, the first available observation will be used in the data summaries and all observations will be presented in the data listings.

Start of treatment refers to the first drug intake and will be identified based on the eCRF entry.

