Time to event: The randomization date (for randomized but not treated subjects) /start of study treatment (for treated subjects) will be used as the start date for the calculation of time to event. Therefore, the time of event will be defined as "date of event – randomization date (for randomized but not treated subjects) / start of study treatment (for treated subjects) +1".

Unscheduled Assessments: Extra assessments (e.g. laboratory data or vital signs) associated with non-protocol visits will be included in listings, but not in the summary tables or figures, unless specified otherwise.

version 3.0 Page: 26 of 87

Definition of phases: The following phase definitions are used for displaying treatment duration, compliance, exposure and adverse events. The two phases in the Part A of the study represent the approximately first 12 weeks of the study, in which participants receive either placebo or elinzanetant 120mg and the approximately 14 weeks when all participants receive elinzanetant (i.e. the participants in the placebo arm will switch to elinzanetant). The start and end date of the phases is defined as following:

- Phase 1 (Part A):
 - Start date = start of treatment for treated subjects / randomization date for subjects, randomized, but not treated
 - \circ End date = first day of phase 2 study drug intake 1 day (based on the eCRF entry)

(For participants who stayed in the study for at least 12 weeks and received the phase 2 study drug);

OR

(For participants who have not received the drug phase 2 due to early discontinuation of randomized treatment or study withdrawal)

Week 12 assessment date or the post treatment phase end date, whichever is earlier

(this is for participants who discontinued from study drug but agreed to complete the assessments until Week 12)

or

Study drug discontinuation date or EoT assessment date, whichever is later (For participants who discontinued from randomized study drug before receiving phase 2 study drug and decided to go to the follow up period or withdraw from the study).

Note: HFDD morning diary and PRO questionnaires which were completed one day after the phase 1 end date will be assigned to phase 1. For participants who were randomized but not treated, the end date = randomization date.

- Phase 2 (Part A):
 - Start date = first day of phase 2 study drug intake (identified based on the eCRF entry)
 - End date = Visit T9 date (For participants who completed the phase 2/Part A, i.e. 26 weeks)
 or

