4.5.3.4. Clinical laboratory

The tabulation of clinical laboratory data will be presented by treatment group for each visit according to the Bayer Global Standard Tables catalogue (version 4.0 or later). It includes:

- Summary statistics of continuous laboratory parameters, and their changes from baseline
- Frequency tables for categorical laboratory parameters

The distribution of laboratory values by treatment group for each visit will be presented graphically with boxplots. Line plots depicting the mean change from baseline \pm 95% CI will be provided for CK, LDH, estradiol, HbA1c, total cholesterol, HDL, LDL and TG and for liver parameters: AST, ALT, ALP, Total bilirubin and INR.

Treatment-emergent (i.e. 14 days from the last drug intake) high and low laboratory abnormalities will be summarized for Week 1-12, 13-26, 27-52 and overall week 1-26, 27-52 and 1-52 by study drug. Both scheduled and unscheduled laboratory measurements will be used in treatment-emergent abnormal laboratory tables.

Central laboratory will be considered for descriptive analysis. Local laboratory measurements will be listed, if available.

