• Tables and figures representing liver monitoring (Section 4.5.3.4.1 in the SAP v3.0) will be shown by week 1-12 and by treatment group (elinzanetant 120 mg and placebo) and by week 1-52 (elinzanetant 120 mg). In addition, exposure adjusted incidence rates per 100 person-years will be calculated.

Formula for exposure adjusted incidence rate = (number of participants with event / sum of exposure days) * 100.

Where sum of exposure days = sum of time to first event for participants if an event occurred + sum of treatment duration with time after treatment up to end of observation for participants without event. Results are provided per 100 person-years, where one person-year is defined as 365.25 days.

- Tables for the following (Sections 4.5.3.6, 4.5.3.7, 4.5.3.9 in the SAP v3.0):
 - Breast imaging Mammogram/Ultrasound
 - o Transvaginal ultrasound
 - Endometrial biopsies

will be shown by treatment group, in addition end of treatment (EoT) and unscheduled visit will be divided into week 1-12 and week 13-52.

In addition, adverse events (AEs) related to abuse potential, including drug abuse and dependence, as well as drug withdrawal, that occur while on-treatment and post-treatment will be presented. AEs will be categorized by primary System Organ Class (SOC) and Preferred Terms (PTs) for Week 1-12, 13-26, 27-52 and overall week 1-26 and 1-52 by study drug. Ontreatment AEs are defined as AEs with an onset between first and last study drug intake date. For abuse potential, post-treatment AEs are all AEs with an onset after the last study drug intake date. Events are assigned to the study drug the participant received last.

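### Laboratory abnormalities that arise on placebo and persist past the switch are also counted under elinzanetant in the by-study-drug tables, because the SAP states no new-or-worse condition and no pre-switch reference value

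*SAP*

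**What the plan says.** **Baseline.** SAP 4.1.2 defines it as "The latest available valid measurement excluding unscheduled measurements at or before the start of treatment (for treated subjects"). The same section adds: "Start of treatment refers to the first drug intake and will be identified based on the eCRF entry". The protocol synopsis describes the second arm as "Placebo for 12 weeks, followed by elinzanetant for 40 weeks", so for that arm the first intake is placebo.

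**Laboratory tables.** SAP 4.5.3.4 states: "Treatment-emergent (i.e. 14 days from the last drug intake) high and low laboratory abnormalities will be summarized for Week 1-12, 13-26, 27-52", continuing "overall week 1-26, 27-52 and 1-52 by study drug. Both scheduled and unscheduled laboratory measurements will be used". By-visit laboratory summaries, changes from baseline and plots are by treatment group.

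**Phases.** SAP 4.1.2 separates placebo-controlled from all-active time, but for listed purposes only: "The following phase definitions are used for displaying treatment duration, compliance, exposure and adverse events". Laboratory data are not on the list, and no phase-specific baseline is given.

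**Liver tables.** SAP 4.5.3.4.1 gives categories by treatment group, some as multiples of ULN and some as multiples of baseline. Section 1 of both SAP supplements adds displays for Weeks 1-12 by treatment group and "by week 1-52 (elinzanetant 120 mg"), without defining a further baseline.

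**The concern.** A table by study drug should show what was newly observed while women took that drug. For adverse events the SAP secures this: 4.5.2 requires occurrence or worsening, and the date imputation in 4.1.1 distinguishes the start of active treatment from the start of placebo. For laboratory abnormalities it states neither a new-onset condition nor a reference value for the switched period.

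The gap matters because there is no placebo comparator after Week 12, so the elinzanetant rows for Weeks 13-26 and 27-52 are read on their own. Increased liver enzymes are also a named risk in protocol 2.3.1. The supplements were written to tell safety events in the placebo-controlled phase apart from those arising once everyone receives elinzanetant, and carried-over abnormalities blur that distinction.

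**Working it through.** **Step 1: apply the stated rule to one case.** Take a woman randomised to placebo with a normal ALT before placebo, a high ALT at T6 before her first elinzanetant capsule, and a high ALT still at T7 (Week 16). The Week 13-26 elinzanetant row could be built in three ways:

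- Any out-of-range value in the window counts: she is counted.
- The study baseline must be normal: it was, before placebo, so she is counted.
- The value must be new or worse than the last one before elinzanetant: she is not counted.

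Only the third rule keeps her out, and the SAP does not state it. She is also counted under placebo for Weeks 1-12 if her T6 value, or an earlier high one, is assigned to that period.

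**Step 2: the period of the T6 sample.** Under SAP 4.1.2, Phase 1 ends the day before the first Phase 2 intake. The protocol's Table 1-2 dispenses drug at T6, and protocol 6.1 has it generally taken at bedtime. A T6 sample drawn before that dose can therefore fall on the first day of Phase 2. The SAP returns the morning diary and questionnaires completed that day to Phase 1 but gives no rule for blood samples. Table 1-2 also sets the T6 window at Days 85-90, while SAP Table 1-2 equates Weeks 1-12 with Days 1-84, so a split by calendar day does not settle the matter either.

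**Step 3: reproduce the plan's completer counts** (SAP 5: 270 and 135 randomised, 10% drop-out in the first 3 months).

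- Elinzanetant: 270 × 0.9 = 243, as stated.
- Placebo: 135 × 0.9 = 121.5, stated as approximately 122.
- Total who can enter Weeks 13-26 on elinzanetant: 243 + 122 = 365.
- Share who are switched women: 122 / 365 = 33.4%.

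**Step 4: size of the carry-over.** Let p be the share of switched women with an abnormality in a given parameter that arose on placebo and persists into Weeks 13-26. Women carried over = 122 × p; addition to the row = 122 × p / 365. The documents give no value for p, so the range is an assumption.

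| Assumed p | Women carried over | Added to Week 13-26 elinzanetant row |
|---|---|---|
| 2% | 2.4 | 0.7 percentage points |
| 5% | 6.1 | 1.7 percentage points |
| 10% | 12.2 | 3.3 percentage points |

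**Step 5: illustration.** Assume true new onset on elinzanetant of 5% in both groups, and p = 5%.

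- As written: [243 × 0.05 + 122 × (0.05 + 0.95 × 0.05)] / 365 = 24.045 / 365 = 6.6%.
- With a new-or-worse rule: [243 × 0.05 + 122 × 0.95 × 0.05] / 365 = 17.945 / 365 = 4.9%.

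**Step 6: which outputs are reached.**

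- High/low abnormalities by study drug, Weeks 13-26, 27-52 and the overall elinzanetant rows: affected.
- Supplement liver tables, Weeks 1-52: affected only if switched women are included. Resetting baseline would then correct only the multiples-of-baseline rows. The ULN-multiple rows do not use baseline and need a new-or-worse condition. In the baseline rows the error can also run the other way: a rise from a T6 value below the study baseline is understated.
- Weeks 1-12 by arm, and all tables by randomised group: no carry-over.

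**The case against.** **The missing rule may exist elsewhere.** SAP 4.5.3.4 refers to the sponsor's standard tables catalogue, and table specifications are held separately. Either could contain a new-onset rule for switched women. That stands as a limit on what can be known, but the SAP is the governing text and its stated criterion lets the carried-over case in.

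**The liver tables are largely outside the problem.** This stands. A reader might infer that a woman at or above 3 × ULN on placebo reappears as an elinzanetant case at that threshold in Weeks 13-26. No planned table does this: the ULN categories in 4.5.3.4.1 are by treatment group, and the supplements add only Weeks 1-12 by arm and Weeks 1-52. Such a woman enters the by-study-drug table only as a high ALT. The Weeks 1-52 column may also mean just the randomised elinzanetant arm, which contains no switched women.

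**Serious liver cases are examined individually.** This also stands. A confirmed ALT or AST above 3 × ULN leads to close observation and an adverse event report (protocol 10.5), an individual time-course plot with drug start and stop dates (SAP 4.5.3.4.1), and review by the liver board. Mere persistence is not a new treatment-emergent event under 4.5.2. These safeguards do not correct counts in the summary tables.

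**The error is conservative.** In the high/low tables it adds to the elinzanetant rows. It still misstates what arose on the drug.

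**A T6 reference has its own weakness.** A transiently high T6 value could hide a later sustained elevation. This stands and is a reason to show both references.

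**Conclusion.** The concern holds for the treatment-emergent high/low laboratory tables by study drug after Week 12. As the SAP is written, an abnormality that arose on placebo and persists past the switch is also counted under elinzanetant. The addition to the Week 13-26 row is about one third of the carry-over rate: 0.7 to 3.3 percentage points per parameter for an assumed 2-10%. This rests on the planned completer numbers, on all 365 completers continuing into Weeks 13-26, and on a rate for which the documents offer no anchor.

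A reader might go further and conclude that the trial's main laboratory and liver evidence is biased, or that changes from baseline in switched women are generally measured from the wrong point. The documents do not support either. The controlled evidence is the Week 1-12 comparison, which has no carry-over. By-visit changes are by randomised group, where the study baseline is appropriate and T6 stands next to T7. For the liver tables the point is conditional on who is in the Week 1-52 column.

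This should be corrected: the plan already uses onset-or-worsening logic for adverse events and lacks it here.

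**What to change.** In SAP 4.1.2 and 4.5.3.4, and in the supplement:

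1. For laboratory tables by study drug, and any liver table pooling all elinzanetant exposure, count an abnormality in a participant randomised to placebo as treatment-emergent on elinzanetant only if it is new or worse than her last valid value before the first elinzanetant intake (normally T6).
2. Use that same value as the reference for multiples of baseline in those tables.
3. Assign a T6 sample drawn before the first elinzanetant dose to the placebo period.
4. Say whether the supplement's Week 1-52 elinzanetant column includes switched women.
5. Keep the study baseline for tables by randomised group, and show the by-study-drug results against it alongside, so that a transiently high T6 value cannot mask a later elevation.

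Cost: a short addition to the text, a second baseline flag in the laboratory dataset, and a footnote explaining the two references. No new data are needed, because the T6 and T7 safety samples are already scheduled.

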The mean daily severity during treatment will be calculated for the available days as $[(1 \times number of mild HF) + (2 \times number of moderate HF) + (3 \times number of severe HF)] / (total number of mild, moderate and severe hot flashes on that day). When no HF are reported for a particular day, the mean severity for that day will be set to 0.$

Similar to the frequency, the severity of HF for each week during the treatment period will be calculated using the available data during that particular week. Specifically, for Week 4 Days 22-28 will be used and for Week 12 Days 78-84 will be used (Day 1 corresponds to start of treatment). To obtain the post-baseline severity of HF during a particular week, the weekly data will be aggregated by averaging the mean daily severity of HF of the available days during that week. In case data is missing for more than 2 days within a week, the value for that particular week will be set to missing.

Mean change in severity of moderate to severe HF from baseline to Week 4 and Week 12:

This will be calculated as the difference in the severity of HF at Week 4 or Week 12, respectively, from the baseline value of the severity of moderate to severe HF.

4.1.3. Participant Disposition

The number of participants enrolled, randomized and valid for the FAS and SAF will be summarized overall and by treatment group, region, country and study site. A listing of the participants' assignment to the FAS and SAF and the reasons for exclusion will also be provided by treatment group.

Other summary statistics will include:

- number of screening failures and the reason for failed screening
- number of participants randomized but not treated (overall and by treatment group).
- number of participants who completed the study, i.e., completed all phases (screening, treatment and follow up) of the study including the last visit.

A disposition summary for each study period (screening, treatment (split by Part A (weeks 1-12 and weeks 13-26), Part B (weeks 27-52) and Part C) and follow-up period, see Section 1.2) will be presented summarizing the number of participants starting and completing the respective study period, the number of participants discontinuing it and the primary reason for discontinuation. This will also be presented overall and for each treatment group. The table will include COVID-19 pandemic associated reasons for discontinuation, i.e., the information whether decision for discontinuation was due to participant specific reasons or due to other reasons.

version 3.0 Page: 29 of 87

In addition, the number of participants with important deviations and validity findings will be presented overall and for each treatment group. The frequencies of each important deviation and validity finding will be presented by treatment group and in total.

Additionally, Kaplan-Meier plots for the time from randomization (for randomized but not treated subjects) / start of study treatment (for treated subjects) to the first occurrence of the intercurrent events "Permanent discontinuation of randomized treatment", "Intake of prohibited concomitant medication having impact on efficacy" and "Interruption/discontinuation in intake of adjuvant endocrine therapy" will be provided by treatment group, where applicable. If "Permanent discontinuation of randomized treatment" did not occur by day 84, the participant will be censored at week 12. If "Intake of prohibited concomitant medication having impact on efficacy" or "Interruption/discontinuation in intake of adjuvant endocrine therapy" did not occur by day 84, the participant will be censored at week 12 or at the time of dropping out of the study, whichever occurs earlier.

The number of observed intercurrent events will be summarized by week and by treatment group and overall.

4.2. Primary Endpoints Analysis

The primary efficacy endpoints for this study are:

- Mean change in frequency of moderate to severe HF from baseline to Week 4 (assessed by HFDD)
- Mean change in frequency of moderate to severe HF from baseline to Week 12 (assessed by HFDD)

See definition in Section 4.1.2.1. Definition of Endpoints

